## 9. Outcome measurement/Data analysis

## - Primary outcome

Pain intensity (visual analogue scale)

Shoulder function (shoulder pain and disability index)

## Secondary outcome

(bubble inclinometer)

Muscle strength (hand held dynamometer)

Postural alignment (photogrammetry)

#### - Assessment of efficacy

The assessments that will be used in this study are standard, reliable and commonly used in the clinic. They have very low risk and are safe to be used in clinic. Moreover, the physical therapy intervention that will be used in this study are safe, proven by the previous study to treat the shoulder impingement syndrome and commonly used in the clinic.

# - Assessment of safety

This study does not include any injection or invasive approach, or taking any medications and does not require any modification of patient treatment programs.

Before giving an informed consent, the participants will be asked whether they have any condition listed in exclusion criteria or any other conditions that may preclude participation in any aspect of the study.

The researcher will explain the procedure, purpose, advantages and possible risk of this study. The researcher will demonstrate each test prior to evaluation and will explain the procedures for each intervention. Moreover, the researcher will observe participants' feeling during assessment.

=	MU-CIRB	Mahidol University Central Institutional Review Board (MU-CIRB)	Date Modified 02/08/2016
	Mahidol University Centra	l Institutional Review Board (MU Central-IRB) Study Protocol	Page 13 of 13

## - Statistics to be used or process for data analysis

Data will be analysed by using SPSS version 23. The statistical significance level is set at p-value < 0.05.

- Shapiro-Wilk will be used to examine the distribution of the data
- Descriptive statistics for demographic data, mean and standard deviation for continuous, cumulative frequency for categorical and median for ordinal variables, will be calculated.
- Two-way mixed design ANOVA (two group x four time) for parametric data. If the data are significant the post hoc analysis will be performed using Bonferroni.
- Friedman test if the data are not normally distributed.

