# 5.2 Specific Objective

- 1) To compare the pain intensity between the conventional and the mobilization with movement groups at baseline, after intervention at week 1, week 2, week 3, and week 4.
- 2) To compare the shoulder range of motion between the conventional and the mobilization with movement groups at baseline, after intervention at week 1, week 2, week 3, and week 4.
- 3) To compare the craniovertebral angle and shoulder angles between the conventional and the mobilization with movement groups at baseline, after intervention at week 2, and week 4.
- 4) To compare the shoulder muscle strength between the conventional and the mobilization with movement groups at baseline, after intervention at week 2, and week 4.
- 5) To compare the shoulder pain and disability index scores between the conventional and the mobilization with movement groups at baseline, after intervention at week 2, and week 4.

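### Two unranked primary outcomes share one 0.05 level with no rule for success and no single deciding test, and the non-normal fallback (Friedman) cannot compare the two groups

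*Combined protocol and SAP*

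**What the plan says.** Section 9 (Primary outcome) lists two items, "Pain intensity (visual analogue scale" and "Shoulder function (shoulder pain and disability index", with no order between them.

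Section 9 (Statistics) then sets one threshold: "The statistical significance level is set at p-value < 0.05". The main analysis is "Two-way mixed design ANOVA (two group x four time) for parametric data". The only multiplicity control is "If the data are significant the post hoc analysis will be performed using Bonferroni". The only provision for non-normal outcome data is "Friedman test if the data are not normally distributed".

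Section 5.2 frames every objective as a comparison between groups, with pain and SPADI as separate objectives: "To compare the pain intensity between the conventional and the mobilization with movement groups at baseline, after intervention at week 1" (and then weekly to week 4), and "To compare the shoulder pain and disability index scores between the conventional and the mobilization with movement groups at baseline" (and then at weeks 2 and 4).

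Section 6.3 sizes the trial on SPADI alone, but neither that section nor any other makes SPADI the lead outcome. No section splits the significance level, orders the tests or says what counts as success.

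**The concern.** With 12 participants per group, a split result (one primary significant, the other not) is a realistic prospect. Under the present text it could be called a success, a failure or two separate findings, and the choice could be made after the data are seen. If one significant primary is enough, the chance of a false primary claim exceeds the stated 5%.

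Two further gaps make this harder to settle afterwards. The mixed ANOVA produces a group effect and a group-by-time interaction, and the plan does not say which one decides, so there is no single p-value per outcome to which a rule could apply. And if the data fail the normality check, the prescribed test looks at change over time within participants. It does not compare conventional therapy with conventional therapy plus mobilization.

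**Working it through.** **The plan's own figure.** Section 6.3 gives SPADI means (SD) of 4.6 (5.0) and 0.4 (1.1) and a total of 20. The pooled SD is sqrt((5.0² + 1.1²)/2) = 3.620, so d = 4.2/3.620 = 1.160. With the noncentral t distribution and 10 per group, power is 80.2% one-sided at 0.05 and 68.9% two-sided. The total of 20 is therefore reproduced by a one-sided 0.05 test with 80% power; a two-sided test with 80% power would need 26. The plan states neither sidedness nor power, so both cases are carried below.

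**Reading 1: either primary suffices, one two-sided test each, no true effect on either.** The family-wise error is 1 − P(|Z1| < 1.96 and |Z2| < 1.96). With independent tests this is 1 − 0.95² = 0.0975. The documents give no correlation between the two test statistics, so the values in between are illustrative:

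| Correlation | Two-sided | One-sided |
|---|---|---|
| 0 | 9.75% | 9.75% |
| 0.3 | 9.5% | 9.3% |
| 0.5 | 9.1% | 8.8% |
| 0.7 | 8.3% | 8.0% |
| 0.9 | 7.0% | 6.8% |
| 1 | 5.0% | 5.0% |

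Section 7 (Research Equipment, item 6) says that patients rate pain as well as disability on SPADI. The two primaries therefore overlap in content, and correlation 0 is a limit and not a likely value.

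**Reading 2: both primaries required.** A false claim needs a significant result on at least one outcome with no true effect. With one test per outcome at 0.05, that has probability at most 5%, and no adjustment is needed. This depends on there being one test. Suppose that SPADI truly improves and is almost sure to be significant, that VAS does not improve, and that either the group effect or the interaction may count. Under normality and compound symmetry the two ANOVA tests are independent, so VAS is falsely significant with probability 1 − 0.95² = 0.0975. Simulation agrees: 0.093 to 0.101 within one outcome (40,000 null trials per setting, 10 and 12 per arm, the Section 5.2 schedules, assumed within-subject correlations of 0.3, 0.6 and 0.8).

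**Reading 3: each objective reported separately at 5%, no joint claim.** There is then no family, and no adjustment across outcomes is called for.

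**The non-normal fallback.** Friedman ranks each participant's repeated measurements against one another. Group membership does not enter the statistic. Applied to all participants, it tests change over time; applied within each group, it gives two separate within-group results. Neither is the between-group comparison that Section 5.2 asks for.

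**The case against.** The strongest reply is that the plan never defines trial success or a joint efficacy claim. Section 5.2 lists pain and SPADI as separate objectives, and on a plain reading each is answered on its own terms, with nothing to inflate. That reading is tenable. But the plan calls both outcomes primary and does not say that they stand alone, so one sentence is still needed.

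It can also be said that two primaries may both be required, which removes the inflation. That is right only once one deciding test per outcome is fixed.

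A reader might infer that the trial's false-positive rate is 9.75%, or higher still by letting either ANOVA effect count on either outcome. The documents do not support this. They do not say that either outcome suffices or that either effect counts, and the overlap in content between SPADI and VAS makes independence unlikely. A reader might also infer from Section 6.3 that SPADI is the lead outcome. The plan does not say so, and Sections 5.2 and 9 both list pain first.

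Finally, part of any fix is preference. Putting SPADI first is one choice among several, and a week 4 test leaves the weekly pain comparisons outside the deciding analysis. Both points stand, which is why the alternatives are given and the ANOVA is kept as supportive.

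**Conclusion.** The point holds as a missing rule, not as a demonstrated error rate. Two unranked primaries are tested at 0.05 with no statement of what counts as success and no single deciding test for either. The consequence depends on the reading:

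- Either suffices, one two-sided test each: family-wise error between 5% and 9.75%, the top being a limit at correlation 0.
- Both required: at most 5% with one fixed test per outcome; up to about 10% if the group effect or the interaction may count.
- Each objective alone: no family to control.

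The Friedman defect does not depend on the reading. Followed as written, the fallback would leave the between-group objectives unanswered. Both matters should be settled before the data are analysed. They affect how the primary result can be read, and the remedy is a change of text.

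**What to change.** In Section 9 (Statistics):

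1. Name one deciding between-group test per primary outcome, for example the baseline-adjusted group difference at week 4, a visit that both outcomes share in Section 5.2. Keep the mixed ANOVA as supportive for the weekly comparisons. Say whether tests are one- or two-sided.
2. Replace Friedman with a between-group alternative, such as the Mann-Whitney test on change from baseline to week 4.
3. State one success rule. For example: SPADI, on which the trial was sized, is tested first at 0.05, and VAS pain at 0.05 only if SPADI is significant. Alternatives are Holm across the two p-values, or both required using the single test in item 1. If each objective is meant to stand alone, say so and make no joint claim.

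**Cost.** A few sentences, with no extra patients or visits. Under the fixed sequence SPADI keeps its full 0.05 level, but a VAS claim depends on SPADI. Under Holm the smaller p-value must be below 0.025. On the Section 6.3 inputs, SPADI power then falls at worst (when VAS does not pass first) as follows:

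| Per arm | Two-sided | One-sided |
|---|---|---|
| 10 | 69% to 57% | 80% to 69% |
| 12 | 78% to 67% | 87% to 78% |

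These are equal-variance t-test illustrations on inputs from an immediate-effects comparison with sham. Requiring both outcomes also costs power, by an amount that the documents do not allow to be computed.

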### 6.3 Sample size

Sample size calculation will be performed using formula for the test of different between 2 independent means.

According to the G\*power 3.1.9.2 program calculation, the total of this study equal 20 subjects. Based on the previous study using the shoulder pain and disability index to measure the shoulder function, in the study of comparing the immediate effects of mobilization with movement and sham techniques. The mean (standard deviation) between group post-intervention for the mobilization with movement group was 4.6 (5.0) and that for the sham group was 0.4 (1.1) (12). In this proposed study, we need equal number of participants per group; therefore, the drop out calculation of 20% from the total participants (n = 1/1-20%). Therefore, after the ethical approval, the researcher will collect data from 24 shoulder impingement syndrome patients (12 subjects on the conventional group and 12 subjects on the mobilization with movement group).

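### For non-normal data the plan has no between-group test, because its only fallback is Friedman; for normal data the deciding ANOVA term is not named

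*Combined protocol and SAP*

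**What the plan says.** The statistics paragraph of section 9 has one model for all normally distributed outcomes: "Two-way mixed design ANOVA (two group x four time) for parametric data". It continues: "If the data are significant the post hoc analysis will be performed using Bonferroni". For other data it says only: "Friedman test if the data are not normally distributed". Normality is to be examined with Shapiro-Wilk, and significance is set at p < 0.05. No other test appears in the document.

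Section 5.2 frames all five objectives as comparisons of the conventional and mobilization groups. Pain and range of motion are compared "at baseline, after intervention at week 1, week 2, week 3, and week 4". Posture, strength and the shoulder pain and disability index (SPADI) are compared "at baseline, after intervention at week 2, and week 4".

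SPADI is one of two primary outcomes in section 9 ("Shoulder function (shoulder pain and disability index"), and the sample size in section 6.3 was built on it ("Based on the previous study using the shoulder pain and disability index to measure the shoulder function").

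**The concern.** An analyst who follows the plan to the letter meets three difficulties of unequal weight.

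1. **The fallback.** If an outcome is judged non-normal, the prescribed test cannot compare the groups. With 12 patients per arm and a normality test as the switch, this branch may well be used. The objective would go untested, or a within-patient result would stand in for a treatment comparison.
2. **The trigger.** The post hoc rule does not say whether group, time or group-by-time must be significant. Under section 8 both arms receive active conventional therapy, so both may improve. A time effect shared by the arms would satisfy the rule and say nothing about the added mobilization.
3. **The time factor.** Four levels fit none of the five schedules. This is an inconsistency to correct, but it does not by itself produce a wrong result.

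**Working it through.** **Inputs.** From the documents: the schedules (section 5.2), 12 per arm (section 6.3) and alpha 0.05 (section 9). Assumed for the simulations: normal data, complete follow-up, SD 1 at each visit, and equal within-patient correlation rho of 0.3, 0.5 or 0.7.

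**Step 1. Time levels.** Counting visits in objectives 1 to 5 gives 5, 5, 3, 3, 3; none is 4. With N = 24 and k times, the interaction has (k − 1) and (k − 1)(24 − 2) degrees of freedom, and there are k(k − 1)/2 pairs of times.

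| k | Interaction df | Pairs | Fits |
|---|---|---|---|
| 3 | 2 and 44 | 3 | SPADI, strength, posture |
| 4 (as written) | 3 and 66 | 6 | no outcome |
| 5 | 4 and 88 | 10 | pain, range of motion |

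**Step 2. The Friedman fallback.** Friedman ranks each patient's values across the k times and compares the rank sums between times. Group membership does not enter, whether it is run on all 24 patients or arm by arm, so it makes 0 between-group comparisons. This needs no assumption. A simulation (3 or 5 times, 4,000 trials per setting) shows what the gap means:

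| True situation | Friedman, pooled | Group-by-time interaction | Mann-Whitney on change to last visit |
|---|---|---|---|
| Both arms improve equally by 1.5 SD | 99.7-100% | 4.8-5.8% | 4.1-5.1% |
| Arms move in opposite directions by 0.8 SD | 1.6-3.4% | 83-99.6% | 86-99.7% |

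The first Friedman entry is power for a true time effect and is not an error in itself. The second shows that Friedman can miss a group difference completely.

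**Step 3. The unnamed term.** If either the group or the interaction term may count, each at 5%, the false-positive rate is 1 − 0.95² = 0.0975, or 9.75% per outcome. Simulation (40,000 trials per setting) gives 9.6-10.0%, with each term alone at 4.8-5.2%. The choice also affects power. If one arm gains an extra 1 SD by the last visit, the interaction is significant in 41-79% of trials and the group main effect in 27-43%.

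A time effect that merely opens the between-group tests does not inflate error. Bonferroni-corrected between-group t-tests at the post-baseline visits give 3.7-4.9% with no gate and 0.2-4.7% when opened by the time term.

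**Step 4. If within-arm change were read as a group difference.** Suppose both arms improve equally and the baseline-to-week-4 paired t-test is Bonferroni-corrected for all pairs of times (10 or 3). If p is its power in one arm, it is significant in exactly one arm with probability 2p(1 − p), which is at most 0.5. Simulated percentages for rho 0.3 / 0.5 / 0.7:

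| Common improvement | Five times | Three times |
|---|---|---|
| 0.5 SD | 10.7 / 16.0 / 28.3 | 23.0 / 31.1 / 43.9 |
| 1 SD | 45.4 / 49.7 / 31.3 | 49.2 / 39.4 / 13.1 |
| 1.5 SD | 33.6 / 14.3 / 1.0 | 15.1 / 3.8 / 0.1 |
| 2 SD | 5.0 / 0.5 / 0.0 | 0.9 / 0.0 / 0.0 |

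The range is about 0% to 50%, governed by an improvement that no document gives. With an error term pooled over the arms (22 df instead of 11), the 1 SD figures at rho 0.7 fall to about 17% and 7%.

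**The case against.** **Time levels.** Section 5.2 fixes the visits outcome by outcome, and an analyst would enter the five or three that exist. Four may also be loose wording for the four weekly assessments. This largely stands. The loose reading could suit pain and range of motion, but it drops a baseline that section 5.2 lists as a comparison time and leaves the other three outcomes with two levels. Even so, no wrong result follows. A reader might infer that the primary analysis cannot be carried out at all; the documents do not support that, because section 5.2 supplies the levels. The flow chart is not reproduced in the text available and could not be checked.

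**Deciding term.** Every objective is between-group, so the purpose of the model is clear, and no section announces an either-term rule or says that within-arm change will be reported as a treatment effect. This stands too: the text is ambiguous but plans no error. It would be wrong to infer that the trigger itself inflates the false-positive rate (step 3), or that the trial carries a false-positive risk of 11-50%. That range appears only if common improvement is capped at 1 SD. Larger standardized change is plausible for pain: entry is limited to 4-7 cm (section 6.2.1), so if the baseline measure stays in that range its SD cannot exceed (7 − 4)/2 = 1.5 cm.

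**Friedman.** No comparable defence is available. No other group test appears in the document, and neither a pooled nor a per-arm Friedman answers any objective.

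**Conclusion.** The point holds, with the Friedman fallback at its centre. As written, any outcome judged non-normal, including either primary outcome, would have no between-group test. That rests on the text and on the definition of the test, with no assumption.

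The unnamed ANOVA term is a real ambiguity of smaller weight. It costs 9.75% against 5% per outcome only if either term is allowed to count. The one-arm-only rates of about 0-50% illustrate a misreading that the text leaves open; they do not estimate this trial's error rate. The four-level time factor is a consistency correction.

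**What to change.** Replace the ANOVA, post hoc and Friedman lines in section 9 with wording such as:

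> Mixed ANOVA is 2 groups x 5 times (baseline, weeks 1-4) for VAS and range of motion, and 2 groups x 3 times (baseline, weeks 2 and 4) for SPADI, strength and posture. The group-by-time interaction alone decides whether the groups differ. Bonferroni-corrected between-group comparisons at the post-baseline visits only locate the difference and are not a second hurdle. If data are not normally distributed, the groups are compared with Mann-Whitney tests on change from baseline at each scheduled post-baseline visit, Bonferroni-corrected across visits. Friedman only describes change over time within a group and is not evidence of a group difference.

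The sentence on the second hurdle matters. If a claim needed both a significant interaction and a significant follow-up test, the simulated false-positive rate would drop to 0.5-1.3%, far stricter than the planned 5%.

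Naming week 4 as a single primary visit is an optional choice for the sponsor; no section does so now.

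The cost is wording only, with no new data, visits or participants. Two downsides remain. The Bonferroni-corrected Mann-Whitney tests are slightly conservative. The interaction is also not always the more powerful term: with five times and rho 0.3, an extra 1 SD gain by the last visit was detected in 40.9% of trials by the interaction and 42.7% by the group term.

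### The planned mixed ANOVA would discard participants who have a week-4 pain score but missed one interim visit, and no sphericity correction is named

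*Combined protocol and SAP*

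**What the plan says.** The statistics paragraph of section 9 is the whole inferential plan. It specifies a Shapiro-Wilk check, then a "Two-way mixed design ANOVA (two group x four time) for parametric data", then "If the data are significant the post hoc analysis will be performed using Bonferroni", with a Friedman test for non-normal data. "Data will be analysed by using SPSS version 23" and "The statistical significance level is set at p-value < 0.05" complete it. It names no analysis population, missing-visit rule, sphericity check or epsilon correction.

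Section 9 lists "Pain intensity (visual analogue scale)" as a primary outcome beside SPADI. Section 5.2 schedules pain and range of motion "at baseline, after intervention at week 1, week 2, week 3, and week 4", which is five times. It schedules posture, strength and SPADI at three times (baseline, weeks 2 and 4). Neither count matches four.

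Section 6.3 states that "the total of this study equal 20 subjects" and raises this to 24 (12 per arm) for 20% dropout. Section 6.4 rules out replacing withdrawals, because that allowance is already in the number.

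**The concern.** A classical repeated-measures ANOVA needs every cell filled for each participant. A person who stays in the trial and has an end-of-treatment score therefore leaves the analysis because of one missed interim week. This differs from withdrawal, which sections 6.2.3 and 6.3 address. With 12 per arm and no replacement, a few such exclusions matter. If missed visits are related to pain, the complete-case comparison may also be biased.

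The second gap concerns the within-subject tests (time and group-by-time). Their uncorrected F tests assume sphericity. Weekly pain scores are plausibly more alike at adjacent weeks, which breaks that assumption. The plan checks only normality and does not say which row of the output governs.

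**Working it through.** **The plan's own figure.** Section 6.3 gives 4.6 (5.0) against 0.4 (1.1) on SPADI. So d = 4.2 / √((5.0² + 1.1²)/2) = 4.2 / 3.62 = 1.16. A two-sample t test needs 10 per arm (20 in all) for 80% power at one-sided 0.05 (power 0.802). At two-sided 0.05, 20 participants give 0.689. The stated 20 is thus reproduced only as a one-sided test at 80% power; neither setting is stated. It serves here only as the plan's target for analysable participants. The stated 24 equals 20 × 1.2.

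**Complete-case loss for pain.** Inputs: 24 enrolled (section 6.3), four post-baseline visits (section 5.2), baseline always observed. The miss probability p per visit, and independence between visits, are assumptions.

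- Analysed by the ANOVA: 24(1−p)⁴
- Week 4 observed: 24(1−p)
- Week 4 observed but discarded: the difference

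| p | Analysed | Week 4 observed | Discarded despite week 4 |
|---|---|---|---|
| 2% | 24 × 0.9224 = 22.1 | 23.5 | 1.4 |
| 5% | 24 × 0.8145 = 19.5 | 22.8 | 3.3 |
| 10% | 24 × 0.6561 = 15.7 | 21.6 | 5.9 |

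With no withdrawals at all, the binomial chance that fewer than 20 are analysed is 3% at p = 2%, 47% at 5% and 95% at 10%. If dropout has already reduced 24 to 20, a 5% miss rate leaves 20 × 0.8145 = 16.3.

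Two variations reduce the loss. If the same people miss every visit (full clustering), nobody with a week-4 score is discarded. If one interim week is left out to make four times, the discarded numbers become 24(1−p) − 24(1−p)³ = 0.9, 2.2 and 4.1.

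**Sphericity.** Null trials were simulated with 12 per arm, equal variances and no missing data (20,000 to 40,000 per case). The uncorrected group-by-time F was tested at 0.05. The covariance is assumed, since the documents give none. Ranges cover repeated runs.

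| Times | AR(1) correlation 0.5 | 0.7 | 0.8 |
|---|---|---|---|
| Five (pain, range of motion) | 6.0–6.4% (ε 0.81) | 6.9–7.1% (ε 0.69) | 7.3–7.5% (ε 0.63) |
| Four (section 9 layout) | 5.7–5.8% (ε 0.86) | about 6.3% (ε 0.77) | 6.5–6.9% (ε 0.72) |

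With three times (SPADI) the rate is about 5.3% to 5.7% over the same correlations. At correlation 0.9 with five times it reaches 8.0–8.3%. Under compound symmetry (ε = 1) it is 5.0% with five times and 5.2% with four. In the AR(1) cases run at 0.5, 0.7 and 0.9 with four or five times (10 or 12 per arm), Greenhouse-Geisser gave 4.2–4.9% and Huynh-Feldt 5.0–5.5%.

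**The case against.** **Is the F test liberal as a matter of fact?** A reader might infer so, but the documents do not support it. They give no covariance, the test is nominal under compound symmetry, and nothing says the uncorrected row governs. SPSS prints the corrected rows beside it. What stands is an unstated choice that could be made after seeing the data.

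**Does the 4–7 cm VAS entry rule itself break sphericity?** This is tempting but weak. With a baseline SD of 0.9 against 1.8 later and a constant correlation of 0.6, ε is 0.98 and the error rate 5.0%. Serial correlation drives the inflation.

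**Does the inflation reach the conclusions?** It affects the time and group-by-time tests, not the group main effect. The post hoc step also limits it. If post hoc means group comparisons at each visit, then with five visits and AR(1) 0.7 a significant interaction plus any difference at 0.05/5 occurred in 1.3% of null trials, against 7.2% for the interaction alone. That protection does not cover a claim drawn from the interaction itself.

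**Is 18.5% of the sample lost at a 5% miss rate?** 1 − 0.95⁴ = 18.5% includes people who missed week 4 itself. The loss peculiar to the method is 3.3 of 24. Missed scores may also mean missed therapy and so cluster, which reduces it further.

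**Would a smaller repair do?** A stated epsilon correction would close the sphericity gap. A missing-visit rule could address the other, but the ANOVA still cannot use incomplete participants without imputation.

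**Conclusion.** The complete-case problem stands and needs no covariance assumption: as written, the analysis discards observed week-4 pain scores. Its size depends on an assumed miss rate and on independence: about 1.4, 3.3 or 5.9 of 24 at 2%, 5% or 10% per visit, down to none if misses cluster fully. At 5%, the expected number analysed (19.5) is already just below the target of 20 before any dropout.

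The sphericity point stands only conditionally. If the uncorrected row is used and scores are serially correlated at 0.5 to 0.8, the group-by-time test runs at about 6% to 8% with five visits, 6% to 7% with four, and little above 5% with three.

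A change should be made before analysis. Neither part shows that the result would be wrong.

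**What to change.** In section 9, replace the ANOVA by a linear mixed model for repeated measures (SPSS MIXED) on all observed post-baseline visits. Use group, visit, group-by-visit and baseline as terms, an unstructured covariance with a simpler structure named in advance as fallback (for example heterogeneous AR(1)), and Satterthwaite degrees of freedom. Report the baseline-adjusted group difference with a 95% CI at each post-baseline visit listed in section 5.2, with week 4 as the end-of-treatment contrast. Making week 4 the only result would go beyond the plan, because section 5.2 lists every visit and names no primary time.

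Reconcile the four times in section 9 with the five for pain and range of motion and the three for the other outcomes. If the ANOVA is kept as a supporting analysis, state that the Greenhouse-Geisser or the Huynh-Feldt row governs, and how missed visits are treated.

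The cost is a rewording of section 9; no extra data are needed, since baseline is already collected. The downside is more covariance parameters in a small sample: unstructured over four visits means 4 × 5 / 2 = 10, estimated from 20 to 24 people. The fallback rule therefore has to be fixed in advance. The mixed model still assumes that missingness depends only on observed data.

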Another study conducted by Tey et al evaluated the immediate effects of mobilization with on shoulder range of motion and pressure pain threshold in people with painful limitation of shoulder movement. The results showed that the mobilization with movement reduced pain and improved range of motion.

Moreover, a randomized controlled trial conducted by Delgado et al showed that the short-term effects of mobilization with movement was effective to decrease pain intensity and increase shoulder range of motion. However, Guimarães et al compared the immediate effects of mobilization with movement with sham technique on shoulder range of motion, muscle strength and function in the patients with shoulder impingement syndrome. The results showed that the mobilization with movement was no more effective than sham technique in improving shoulder external rotation and abduction, pain and function. These different results lead this study to compare the effects of adding mobilization with movement on the conventional treatment.

Several outcomes have been commonly investigated in the shoulder impingement syndrome-related previous research, for example, pain intensity, shoulder range of motion, muscle strength, and shoulder function. The pain intensity was usually assessed using the visual analogue scale. The shoulder range of motion was assessed using a bubble inclinometer, the shoulder muscle strength, and function were investigated using hand held dynamometer (HHD) and a self-reported questionnaire e.g. shoulder pain and disability index, respectively.

MU-CIRB	Mahidol University Central Institutional Review Board (MU-CIRB)	Date Modified 02/08/2016
Mahidol University Centra	ll Institutional Review Board (MU Central-IRB) Study Protocol	Page 3 of 13

Since the postural correction exercise is commonly applied in the conventional physical therapy, neck and shoulder posture can be assessed using photogrammetry measurement. The neck and shoulder posture can be generally assessed by measuring the craniovertebral angle and shoulder angles, respectively.

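### Between-group follow-up depends on a significant ANOVA, and no difference or confidence interval is planned for pain or SPADI, so a null result would come without an estimate

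*Combined protocol and SAP*

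**What the plan says.** The whole analysis plan is the short list under the statistics heading of section 9. Apart from a normality check and the significance level, it holds three things relevant here.

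- **Main analysis.** "Two-way mixed design ANOVA (two group x four time) for parametric data", followed by the condition "If the data are significant the post hoc analysis will be performed using Bonferroni". No ANOVA term is named as the one that must be significant, and no contrast, effect size or interval is named.
- **Fallback.** "Friedman test if the data are not normally distributed".
- **Summaries.** "Descriptive statistics for demographic data, mean and standard deviation for continuous, cumulative frequency for categorical and median for ordinal variables, will be calculated".

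Section 5.2 is not conditional. Its first objective, which ends with the week 4 visit, opens: "To compare the pain intensity between the conventional and the mobilization with movement groups at baseline, after intervention at week 1, week 2, week 3,". The SPADI objective has the same form at baseline, week 2 and week 4. Section 9 names pain intensity and SPADI as the primary outcomes. Section 4 gives the reason for the trial: earlier studies conflict, and "These different results lead this study to compare the effects of adding mobilization with movement on the conventional treatment".

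**The concern.** The objectives ask how the arms compare at each visit. The analysis section supplies a between-group comparison only after a significant test, and even then names only a Bonferroni procedure. The Friedman test ranks visits within a patient, so that route gives no between-group estimate at all.

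The trial was prompted by conflicting earlier results, one of them a finding of no advantage over a sham. A further null reported as a p-value, with 10 to 12 patients per arm, would not show which effects it rules out. Readers could then take it as evidence that mobilization adds nothing when the data remain compatible with a large benefit.

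**Working it through.** **Inputs from section 6.3.** SPADI 4.6 (SD 5.0) with mobilization and 0.4 (SD 1.1) with sham; 20 patients before dropout; 24 recruited, 12 per arm.

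**Planning effect.** Difference = 4.6 − 0.4 = 4.2. Pooled SD = √((5.0² + 1.1²)/2) = √13.105 = 3.62. d = 4.2/3.62 = 1.16.

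**The plan's own figure.** Power and sidedness are not stated. With alpha 0.05 and an assumed 80% power, a one-sided t-test needs 10 per arm (power 80.2%), which reproduces the total of 20. A two-sided test needs 13 per arm, or 26. The recruited 24 equals 20 × 1.2.

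**Precision of an unadjusted two-arm difference at one visit.** Half-width = t(0.975, 2n − 2) × √(2/n) SDs.

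| Completers per arm | Half-width, SD | SPADI points (SD 3.62) |
|---|---|---|
| 10 | 2.101 × 0.447 = 0.94 | 3.40 |
| 12 | 2.074 × 0.408 = 0.85 | 3.06 |

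For pain, the documents give no SD. If it is 1.5 to 2.5 cm (assumed), the half-width at 10 per arm is 0.94 × 1.5 = 1.4 cm to 0.94 × 2.5 ≈ 2.3 cm, in patients who enter at 4-7 cm.

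**What a null leaves open, at 10 per arm.** An observed SPADI difference of exactly zero still leaves benefits up to 3.4 points inside the interval. Any observed difference above 4.2 − 3.4 = 0.8 points in favour of mobilization leaves the full planned difference inside it. Such a result is non-significant on a two-sided t-test as long as it stays below 3.4 points.

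**How often no contrast would be produced.** This was simulated: 20,000 trials per cell, 10 per arm, compound symmetry, and a difference growing linearly from zero at baseline to d SDs at week 4. The correlations, the linear profile and the d values of 0.8 and 0.5 are assumptions.

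*If the group-by-time term must be significant* (5 visits for pain, 3 for SPADI):

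| True d | No contrast, correlation 0.5 | No contrast, correlation 0.7 | Mean overstatement of week-4 difference among significant trials (0.5; 0.7) |
|---|---|---|---|
| 1.16 | 40-41% | 16-17% | 9-11%; 3-4% |
| 0.8 | 68-70% | 51% | 24-27%; 13-15% |
| 0.5 | 86% | 78-80% | 46-54%; 34-40% |

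With the four time points written in section 9, the no-contrast rates at correlation 0.5 are similar: 42%, 70% and 86%. With all 12 per arm retained and correlation 0.5, the rate at d = 1.16 is about 31%.

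*If any significant term (group, time or interaction) suffices*, with an assumed control-arm improvement of 0.5 SD by week 4: no contrast in at most 0.3% of trials at d = 1.16, about 4% at d = 0.8 and about 14% at d = 0.5. Overstatement is negligible at d = 1.16 and 0.8, and at most about 5% at d = 0.5. With a control-arm improvement of 1.0 SD, the no-contrast rate is 0-0.1% at all three effects.

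**The case against.** Testing an omnibus term first and then contrasts is a common sequence. The plan nowhere says that means or differences will be withheld, and section 5.2 can be read as promising them. The descriptive bullet opens with "Descriptive statistics for demographic data" but continues with types of variable, so it may be meant to cover outcomes too. With means and SDs by arm and visit, a reader could work out the difference and its interval. Both arms also receive four weeks of active therapy, so a time effect is plausible, and on the loosest reading of the condition the follow-up would nearly always be run at the planning effect.

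Much of this stands, and it rules out several stronger conclusions that a reader might draw:

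- *That outcomes will not be summarised at all.* The bullet is ambiguous and does not show this.
- *That a non-significant result is likely.* At the planning effect it is a minority outcome even with group by time as the trigger, at the correlations of 0.5-0.7 assumed here.
- *That any positive result will be inflated.* Inflation is an average over significant trials. It is about 3-11% at the planning effect with the group-by-time trigger and negligible with the loose one. The large figures need smaller effects, which the documents do not give.
- *That reporting every result would correct a positive estimate.* In a trial that meets the condition, the estimate is the same number either way.

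What the objection does not answer is that section 9 states a condition. Neither the ambiguous bullet nor section 5.2 commits to a difference with an interval, and the Friedman route offers none.

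**Conclusion.** The point holds as a gap in planned estimation. Section 9 ties between-group follow-up to significance and promises no difference or interval for pain or SPADI, while section 5.2 sets the comparisons without condition. The consequence that rests least on assumption is precision. At 10 per arm the half-width is 0.94 SD in any case, and 3.4 SPADI points if the planning SD applies, so a null without its interval could be read as no added effect when a large benefit remains possible.

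The frequency is much less certain. It is about 16-41% at the planning effect if group by time is the trigger, higher at smaller effects, and rare at the planning effect if any term suffices. The plan does not settle which applies. Inflation of positive results is a minor, average effect at the planning value and is not the reason for the change. This is an inexpensive improvement that should be made. It does not invalidate the design.

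**What to change.** Keep the Bonferroni adjustment for the post hoc significance tests, so that the plan's multiplicity control is not lost, and add to section 9:

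> For VAS and SPADI the between-group mean difference with its 95% confidence interval will be reported at each post-baseline visit, including week 4 (end of treatment), whatever the ANOVA p-value, with mean (SD) by arm and visit. If data are not normally distributed, a between-group estimate with interval (for example a Hodges-Lehmann difference in change from baseline) will be reported instead. A non-significant result will be interpreted from its interval, not as absence of an added effect.

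The cost is one paragraph of wording. It needs no new patients, visits or data, and the sample size does not change. The only downside is that wide intervals become visible.
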